9.4 STATISTICAL ANALYSIS PLAN

9.4.1 GENERAL APPROACH

Behavioral and brain data analysis will undergo separate analyzing streams to test intervention effects and underlying mechanisms at different time points. Given the scope of this 1-year pilot project, the logical first step at this early stage of research is to examine the potential intervention effects and mechanisms in small sample size, then move to the full scale RCTs for replication. To address our study Aims, repeated-measures ANOVA will be used. By utilizing all assessment points, this approach allows for well-powered tests to detect significant differences in changes across the experimental conditions, even when assuming smaller magnitude effect sizes. Effect size measures (from the repeated-measures ANOVA, Cohen's d highlighting mean differences between treatment and control groups across assessments) will also be calculated to describe the intervention's effect on study outcomes.

9.4.2 ANALYSIS OF THE PRIMARY ENDPOINT(S)

The primary endpoints are behavioral and cognitive assessments and are all repeated measures assessed at baseline, post-intervention, and 3-month follow-up. For cognitive assessment of N-Back working memory, percentage of correct trials will be calculated for each trial for all endpoints. For behavioral assessment of emotion regulation, mindfulness, and SCD, these self-report questionnaires will be calculated based on established scoring guides by summing all items within a given questionnaire for all endpoints. Next, the effects of intervention (IBMT vs. HE) on each of these primary endpoints will be examined using repeated-measures ANOVA with time x group interaction effect. Variance and covariance across repeated measures will be calculated as part of the ANOVA. Age and sex will be included as covariates to control for potential confounding effects of age and sex on behavioral and cognitive assessments. Results will be presented as F values for the interaction effect, along with p values to indicate statistical significance. Normality and homogeneity of variance assumptions will be checked using SPSS built-in tools for ANOVA. Because there are 4 primary endpoints, multiple comparison corrections will be conducted using FDR correction. Missing data will be handled with case-wise deletion.

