3 OBJECTIVES AND ENDPOINTS

| OBJECTIVES | ENDPOINTS | JUSTIFICATION FOR ENDPOINTS |
|--|---|--|
| Primary | | |
| This study aims to investigate the modulation effects of a novel body-mind intervention on behavioral and cognitive outcomes. | Baseline and post-intervention assessments of behavioral and cognitive outcomes (emotion regulation, mindfulness, SCD). | The novel body-mind intervention should lead to improvement in behavioral and cognitive outcomes at post-intervention compared to baseline. |
| Secondary | | |
| This study aims to investigate the modulation effects of a novel body-mind intervention on brain outcomes. | Baseline and post-intervention assessments of brain outcomes (white matter, grey matter, functional connectivity in AD signature regions). | The novel body-mind intervention should lead to improvement in brain outcomes at post-intervention compared to baseline. |
| Tertiary/Exploratory | | |
| N/A | N/A | N/A |

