5.5 STRATEGIES FOR RECRUITMENT AND RETENTION

We anticipate to enroll 40 participants (males and females) ages from 40 to 65 years old across different race and ethnicity based on local demographic characteristics. Subjects will be recruited through print and media ads within local community. This will include radio and online ads and recruitment through social media. Flyers will be distributed throughout the local community. Based on our and other's previous experiences in longitudinal studies, about 5-10% of participants will dropout over the study period due to illness or relocation. We plan a dropout rate of 10% for this brief intervention. We propose to recruit 40 older adults of which 36 (90%) will complete the study.

Compensation and Retention. Participants will be financially compensated with \$300 in total for completing the study protocol (approximately for 15 hours of time); participants who only partially complete the protocol will be compensated based on prorated hours. To maximize participant retention we will maintain contact with participants over time via frequent assessment intervals (e.g., requiring a functioning phone number and email address to contact participants by phone or email as needed, and obtaining the name, address, and phone number of at least 2 friends or classmates who can provide contact information for the participants, should we be unable to contact them during the study; emails and reminder phone calls prior to all study visits; offer flexible scheduling options for assessment (including weekends); provide fair compensation to participants; and maintain positive relations with participants. These procedures were used to maintain adequate participant retention in our prior NIH studies.

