9 STATISTICAL CONSIDERATIONS

9.1 STATISTICAL HYPOTHESES

- Primary Endpoint(s):

We hypothesize that, compared to participants who receive a control intervention, participants who receive IBMT for improving behavior and cognition will have improved working memory, emotion regulation, and reduced subjective report of cognitive decline after completing the intervention at post-assessment, and will continue to show improvement 3 months after the intervention. Alternatively, our null hypothesis is that there will be no difference in the effects of IBMT for improving behavior and cognition and those of control intervention at post-assessment or after 3 months of intervention.

- Secondary Endpoint(s):

We hypothesize that, compared to participants who receive a RT control intervention, participants who receive IBMT for improving brain function and structure will have improved white matter, grey matter, and functional connectivity in AD-signature regions after completing the intervention at post-assessment, and will continue to show improvement 3 months after the intervention. Alternatively, our null hypothesis is that there will be no difference in the effects of IBMT for improving brain function and structure and those of RT at post-assessment or after 3 months of intervention.

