9.2 SAMPLE SIZE DETERMINATION

Our series of RCTs suggest that IBMT showed significant effects in relatively small sample size ¹⁻⁴⁴. For example, a recent RCT in healthy older adults showed significant effects on quality of life (N=25) and in resting state functional connectivity and structural changes in the ACC/mPFC-Striatum networks following IBMT (N=13) ⁴; In adults, we detected significant fMRI signal changes in the ACC/mPFC (Cohen's $d = .90$) after 10-session IBMT ^{9,11}. We used GPower 3.1 software to determine the smallest detectable effect for a treatment X time interaction term given various sample sizes and a power of 0.80, assuming varying correlations between repeated measures, which ranged from .30 -.60 on behavioral and .50 -.80 on fMRI measures in our prior studies ¹⁻⁴⁴. Considering these factors, our target N of 40 after attrition will allow us to detect small-medium-sized effects on continuous outcomes. The N of 40 will provide a reasonable sample to determine the effect size of IBMT without utilizing an unreasonable amount of resources in this pilot. Specifically, 40 subjects will give us adequate statistical power (80%) to detect a medium effect size [$f = 0.3$ for ANOVA and $h = 0.6$ for proportion difference] with alpha=0.05 for analysis proposed. This effect size is conservatively estimated based on our previous studies ^{5,8-12}. The Chi-square test would be less statistically powerful; however, as the nature of this project is exploratory, we are interested in determining the potential effect size of intervention and in developing our intervention protocol in older adults before testing it in a larger sample size.

Given the 1-year project with pre, post-intervention and follow-up and power considerations, the N of 40 we choose is also in line with our intervention cycles and capacities.

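### The primary test is one 2-df time-by-group F with no baseline covariate: it cannot isolate the post-intervention endpoint, Sections 3 and 9.1 disagree on the deciding time, and power is lost

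*Combined protocol and SAP*

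**What the plan says.** Section 9.4.2 lists four primary endpoints (N-Back, emotion regulation, mindfulness, SCD), each measured at baseline, post-intervention and 3 months. The test is stated once for all of them: "each of these primary endpoints will be examined using repeated-measures ANOVA with time x group interaction effect". The covariates are demographic only: "Age and sex will be included as covariates to control for potential confounding effects of age and sex on behavioral and cognitive assessments". The planned output is equally short: "Results will be presented as F values for the interaction effect, along with p values to indicate statistical significance". FDR correction is applied across the four endpoints, and missing data are handled by case-wise deletion.

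Section 9.4.1 adds an effect size, "Cohen's d highlighting mean differences between treatment and control groups across assessments", without a confidence interval.

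Two sections say when the primary question is decided. Section 3 gives "Baseline and post-intervention assessments of behavioral and cognitive outcomes (emotion regulation, mindfulness, SCD", with no 3-month value. The null in Section 9.1 is that the effects of IBMT do not differ from "those of control intervention at post-assessment or after 3 months of intervention".

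**The concern.** There are three linked problems.

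- **The deciding time is not settled.** Section 3 points to post-intervention, and Section 9.1 points to post-assessment and 3 months together. In randomised arms the expected baseline difference is zero, so the time-by-group F does test the joint null of Section 9.1. It does not test the Section 3 endpoint on its own.
- **The F has neither sign nor visit.** The hypothesis in Section 9.1 is directional, but no contrast is specified at any visit. A difference confined to 3 months could be read as meeting a post-intervention endpoint. FDR over four F tests does not cover a later choice of which visit to stress.
- **Baseline is used inefficiently.** It enters as one of three outcomes rather than as a covariate. At moderate correlations this costs power, even against a test of the same two-visit null.

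The stake is a primary result that cannot be read unambiguously, and lower power than the same data could give in a trial expecting 36 completers.

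**Working it through.** **Inputs from the documents.** Two arms, three visits, so interaction df = (3−1)(2−1) = 2. Alpha is 0.05 (Section 9.2). Correlations between repeated measures: "which ranged from .30 -.60 on behavioral and .50 -.80 on fMRI measures in our prior studies" (Section 9.2). Completers: "We propose to recruit 40 older adults of which 36 (90%) will complete the study" (Section 5.5), taken as 18 per arm.

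**Assumptions.** Standardised arm differences v = (d at post, d at 3 months), because the documents give no behavioural SD or mean difference. Compound symmetry with correlation ρ; two-sided tests; no age or sex terms in any test; alpha not adjusted for FDR.

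**The plan's own figure.** Section 9.2 states 80% power at N = 40 for f = 0.3. The usual G*Power interaction formula is λ = f²Nm/(1−ρ), with df (m−1) and (N−2)(m−1). For m = 3 and ρ = .30, λ = 0.09×40×3/0.70 = 15.4, giving 94%. For ρ = .60, λ = 27.0, giving 99.7%. With m = 2 the range is 88–99%. The 80% is not reproduced. On that scale, with pattern (0, d, d), f² = d²/18, so f = 0.3 means d = 0.3×√18 = 1.27. The stated power therefore does not carry over to a d of about 0.6.

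**Formulas at N = 36 (N/4 = 9), with I the 2×2 identity and J the 2×2 matrix of ones.**

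- Planned F: λ = 9·v′[(1−ρ)(I+J)]⁻¹v, df 2 and 68.
- Baseline-adjusted joint test of the same null: λ = 9·v′[(1−ρ)(I+ρJ)]⁻¹v, df 2 and 32.
- ANCOVA at post only: λ = 9·d²/(1−ρ²), df 1 and 33.

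**Worked case, d = 0.6 at both visits.**

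- Planned F: λ = 9×(2/3)×0.36/(1−ρ) = 3.09 at ρ = .30 and 5.40 at ρ = .60. Power 32% and 52%.
- Joint test: λ = 9×2×0.36/[(1−ρ)(1+2ρ)] = 6.48/1.12 = 5.79 and 6.48/0.88 = 7.36. Power 53% and 64% by formula, 51% and 62% by simulation.
- ANCOVA at post: λ = 3.24/0.91 = 3.56 and 3.24/0.64 = 5.06. Power 45% and 59% by formula, 44% and 58% by simulation.

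**Simulated power, 20,000 trials per cell, ρ = .30 to .60.** Noncentral F agrees within about 1 point.

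| d at post, 3 months | Planned F | Adjusted joint test | ANCOVA at post |
|---|---|---|---|
| 0.6, 0.3 | 25–40% | 36–47% | 44–57% |
| 0.6, 0.6 | 32–52% | 51–62% | 44–58% |
| 0.6, 0.9 | 52–78% | 75–86% | 44–58% |
| 0.4, 0.8 | 41–65% | 58–72% | 23–30% |
| 0, 0.8 | 53–78% | 58–78% | 5% |

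Under the null all three tests reject 4.8–5.2% of the time.

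**Reading the table.** The last row shows the isolation problem: the F is often significant when nothing differs at post. Columns two and three are like for like. In these rows the joint test gains from about 1 point (0, 0.8 at ρ = .60) to about 23 points (0.6, 0.9 at ρ = .30). ANCOVA at post beats the F only for fading or flat effects. At ρ = .80 and d = 0.6 at both visits, the three tests give 83%, 85% and 82%, so there is no material gain.

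**Source of the loss.** At N = 40 and d = 0.6, a 1-df change-score test at post has 35% and 54% power, against 35% and 57% for the F when the effect is held to 3 months. The loss comes mainly from not adjusting for baseline, not from the second degree of freedom.

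**The case against.** The strongest reply is that the plan tests what Section 9.1 states. Its null spans both follow-up times, Section 9.4.1 says all assessments are used, and the F fits both. On this reading the only fault is the Section 3 table, which also omits working memory. That would settle the deciding time if the sponsor confirms it, but the documents do not say which section governs. Nor would it supply a direction, a visit-specific estimate or an interval.

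Second, the Cohen's d in Section 9.4.1 could mean one value per assessment, and that section also speaks of testing effects at different time points. This is fair: the wording is ambiguous rather than clearly pooled. Even so, no contrast and no CI are specified.

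Third, the power gain depends on assumed effects. With an effect at one visit only (d = 0.6), it is a few points at ρ = .30 and about 1 or less at ρ = .60. For opposite-signed effects (0.6, −0.1) at ρ = .60 the F can be about 1 point ahead. For d = 0.3 at both visits the F has 11–16% and the joint test 16–19%, neither useful. These limits stand, and confidence in the size of the gain should be lower than confidence in the unnamed contrast.

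Fourth, the figures use alpha .05 and N = 36. Section 9.2 speaks of 40 after attrition, and Section 9.3 requires all 10 sessions and usable data, so the analysed number may differ. At N = 40 and d = 0.6 at both visits the F has 35–57% and ANCOVA at post 49–64%. At alpha .0125 the joint test's advantage for that flat effect at N = 36 remains about 9 to 14 points.

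Finally, this is an exploratory pilot and RM-ANOVA is valid. That limits the severity. But Section 9.2 gives estimating the effect size as an aim, and an F with a p value does not do that.

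**Conclusion.** The concern holds, as something that should be changed rather than a flaw that invalidates the trial. Two parts rest on the text alone: Sections 3 and 9.1 name different deciding times, and Section 9.4.2 plans no signed, visit-specific contrast, so its F cannot isolate the Section 3 endpoint. The third part, lost power, rests on assumed effects and compound symmetry. For same-direction effects at both visits, as tabulated at ρ = .30–.60, the baseline-adjusted test of the same null gains roughly 6 to 23 points. The gain is small when only one visit shows an effect and immaterial at ρ = .80.

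A side point: if the F is left uncorrected for non-sphericity, assumed correlations of .6 between adjacent visits and .3 or .1 between baseline and 3 months give type I error of 5.8% or 6.4%. The documents neither plan nor exclude a correction.

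**What to change.** 1. **Reconcile Sections 3 and 9.1** and name one deciding contrast per endpoint. If Section 3 governs, use the arm difference at Visit 12. If Section 9.1 governs, use the 2-df joint test over both follow-ups, or the difference in the two-visit mean.
2. **Replace the RM-ANOVA in Section 9.4.2** with a longitudinal model. Outcomes: post and 3-month values. Terms: baseline score, baseline by visit, arm, visit, arm by visit, age and sex. Use unstructured covariance, which removes the sphericity issue, and small-sample degrees of freedom.
3. **Apply the planned FDR correction** to that one contrast across the four endpoints.
4. **Report the arm difference at each visit with a 95% CI**, and keep the omnibus F as descriptive.
5. **State the trade-off.** If Visit 12 alone decides, power is lower when benefit emerges later (0.4 then 0.8: 23–30%, against 41–65% for the F).

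The same model can be used in Section 9.4.3 for consistency, without claiming a material power gain at the top of the .50–.80 range.

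The cost is SAP wording and one decision. No new measurement is needed, since Section 9.4.2 already plans all four endpoints at baseline. N-Back is described in Sections 8.1 and 9.4.2 but missing from the Section 1.3 schedule, and should be added there. A standard mixed-model procedure fits the model.

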9.4.3 ANALYSIS OF THE SECONDARY ENDPOINT(S)

The secondary endpoints are brain assessments and are all repeated measures assessed at baseline, post-intervention, and 3-month follow-up. For brain assessment of white matter, white matter integrity metrics will be calculated for all endpoints based on standardized processing pipelines of diffusion-based white matter data using FSL (<http://www.fmrib.ox.ac.uk/fsl>). For brain assessment of grey matter, cortical thickness and volume metrics will be calculated for all endpoints based on standardized processing pipelines of structural MRI data using SPM12 (<http://www.fil.ion.ucl.ac.uk/spm>). For brain assessment of functional connectivity, pair-wise correlations of fMRI timeseries will be calculated for regions of interest and for all endpoints based on standardized processing pipelines of fMRI data using REST software (www.restfmri.net). After these data preprocessing and calculation, numerical values will be generated for all secondary endpoints (white matter, grey matter, and functional connectivity). Next, the effects of intervention (IBMT vs. HE) on each of these secondary endpoints will be examined using repeated-measures ANOVA with time x group interaction effect. Variance and covariance across repeated measures will be calculated as part of the ANOVA. Age and sex will be included as covariates to control for potential confounding effects of age and sex on brain function and structure. Results will be presented as F values for the interaction effect, along with p values to indicate statistical significance. Normality and homogeneity of variance assumptions will be checked using SPSS built-in tools for ANOVA. Because there are 3 secondary endpoints, multiple comparison corrections will be conducted using FDR correction. Missing data will be handled with case-wise deletion.

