1.3 SCHEDULE OF ACTIVITIES

| | Screening | Visit 1 Day 1 | Visit 2 to Visit 11 Day 3 ±1 to Day 12 ±1 | Visit 12 Day 13 ±2 | Visit 13 Day 90 ±2 |
|---|-----------|------------------|--|-----------------------|-----------------------|
| Review Eligibility | X | | | | |
| Informed Consent | | X | | | |
| Demographics | | X | | | |
| Outcome Evaluation | | | | | |
| Behavioral Assessment (Emotion Regulation Questionnaire; Five Facet Mindfulness Questionnaire; Subject Cognitive Decline Questionnaire) | | X | | X | X |
| Brain Assessment (MRI scan) | | X | | X | X |
| Randomization | | X | | | |
| Control & Experimental Interventions | | X | X | | |
| Adverse Events Reporting | | X | X | X | X |

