2.3 RISK/BENEFIT ASSESSMENT

2.3.1 KNOWN POTENTIAL RISKS

The study includes behavioral, cognitive, and brain assessments, as well as mindfulness-based intervention.

Behavioral and Cognitive Assessments

- *Immediate risks: Potential boredom from completing the questionnaires and interviews.*
- *Long-term risks: Data including self-report, questionnaires and interview involve risk of breaches in confidentiality.*
- *Alternative procedures: There are no other available alternative procedures to assess behavior and cognition, since to assess the behavior and cognition, we have to use the actual assessments. To minimize immediate risks, breaks in between questionnaires and interviews are offered to reduce*

boredom. To minimize long-term risks, all information about the specific individuals will be maintained as confidential. Absolutely no names of subjects are used in published reports or in presentations in scientific meetings. All data will be kept in locked files and digital media in the PI's laboratory. Reference to individual subject data will be made with a number and letter code for each subject. Any risks to participants are minimal and are outweighed by the benefits of increasing our scientific understanding of improving cognitive function in older adults.

Brain Assessments

- *Immediate risks: Potential boredom from completing the MRI scan, the possibility of becoming uncomfortable in the enclosed space of the scanner.*
- *Long-term risks: MRI data involves risk of breaches in confidentiality.*
- *Alternative procedures: There are no other available alternative procedures to brain, since to assess the brain, we have to use the actual MRI assessments.*

Mindfulness-based Intervention

- *Immediate risks: Potential boredom from completing the intervention.*
- *Long-term risks: No known risk based on our previous studies ¹⁻¹².*
- *Alternative procedures: There are no other available alternative procedures, since the goal is to test the effects of the mindfulness-based intervention. To minimize immediate risks, breaks during the session are offered to reduce boredom.*

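### Section 9.4.3 drops a participant's valid scans when one of three is unusable, costing the brain endpoints avoidable precision; the size depends on how scans are lost

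*Combined protocol and SAP*

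**What the plan says.** Section 9.4.3 covers white matter, grey matter and functional connectivity: "The secondary endpoints are brain assessments and are all repeated measures assessed at baseline, post-intervention, and 3-month follow-up". Section 1.3 schedules the "Brain Assessment (MRI scan" row at Days 1, 13 and 90. Group effects on each endpoint "will be examined using repeated-measures ANOVA with time x group interaction effect", and "Age and sex will be included as covariates". The missing-data rule is one sentence: "Missing data will be handled with case-wise deletion". The plan names no imputation, mixed model, missingness assumption or missing-data sensitivity analysis.

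Section 9.3 limits the analysis population to participants with all 10 sessions and complete, usable data on the primary endpoints. Those endpoints are behavioral and cognitive, so a participant with a failed scan can be in the population and still be dropped from a brain analysis. Section 9.4.1 justifies repeated-measures ANOVA on the ground that it draws on every assessment point.

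**The concern.** A repeated-measures ANOVA with case-wise deletion needs all three scans. If one is aborted, spoiled or missed, the other two are discarded for that endpoint, although they still carry information on the time by group effect. That runs against the rationale in Section 9.4.1.

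The secondary objective would lose precision in a trial expecting only 36 completers. The three brain tests could also rest on three different subsets of participants. Scan failure is foreseeable: Section 2.3.1 lists "the possibility of becoming uncomfortable in the enclosed space of the scanner" as a risk. If failure were linked to the brain outcome differently in the two arms, the time by group estimate could also be biased.

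**Working it through.** **Inputs from the plan.** Three scans (9.4.3); 36 completers of 40 recruited (5.5), taken as 18 per arm; correlation .50 to .80 for fMRI measures (9.2); "with alpha=0.05 for analysis proposed"; a non-directional test ("Results will be presented as F values for the interaction effect, along with p values").

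**Assumptions.** Loss per scan q = 5, 10 or 15%; compound symmetry; an equal group difference δ (in SD) at Days 13 and 90; deletion applied per endpoint; covariance treated as known; no covariate adjustment.

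**The plan's own figure.** Section 9.2 states 80% power at N = 40 for f = 0.3. For the three-wave interaction, λ = f²·N·3/(1−ρ) with 2 and 2(N−2) df. This gives 94% at ρ = .30, 98.8% at .50 and about 100% at .80. A between-group main effect gives 51 to 72%, and a one-way ANOVA 46%. None of these conventions gives 80%, so δ was set instead to give 80% power with 36 full series.

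**Complete series.** The expected number is 36(1−q)³. The usable scans discarded are 108(1−q) − 108(1−q)³.

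- q = 5%: 36 × 0.857 = 30.9 participants; 102.6 − 92.6 = 10.0 scans discarded.
- q = 10%: 36 × 0.729 = 26.2; 97.2 − 78.7 = 18.5.
- q = 15%: 36 × 0.614 = 22.1; 91.8 − 66.3 = 25.5.

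**Power under deletion.** With the same δ at both follow-ups, λ = δ²N/[6(1−ρ)]. At ρ = .50, δ = 0.916: λ = 0.839 × 36/3 = 10.07, which gives 80%. At q = 10%, λ = 10.07 × 0.729 = 7.34, which gives 65%. Because δ is recalibrated at each ρ (0.767 at .65, 0.579 at .80), the deletion figures are the same throughout the range.

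**Power using every usable scan.** The information on the visit means was summed over all missingness patterns, and the same 2-df contrast was then tested.

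| Independent loss per scan | Deletion | All usable scans | Excess SE under deletion |
|---|---|---|---|
| 5% | 73% | about 77% | about 4% |
| 10% | 65% | about 73% | about 9% |
| 15% | 56% | about 69% | about 14% |

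**Loss at person level.** Let a participant lose all three scans with probability a = q/2, and otherwise lose each scan independently with probability b, where (1−a)(1−b) = 1−q. At q = 10%, a = 0.05 and b = 1 − 0.90/0.95 = 0.053. Complete series are then 36 × 0.95 × 0.947³ = 29.1, and power is 70% under deletion against about 74% with all scans. The gaps at 5/10/15% are about 2/4/7 points. If all loss is at person level, there are no partial series to recover and the gap is zero (75% for both at q = 10%).

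**Bias.** A simulation with ρ = .65, no true effect and roughly 17 to 21% missing gave complete-case bias of about zero in three settings: missing completely at random; missingness depending on age; and missingness depending on an observed scan value equally in both arms. When that dependence was present in one arm only, bias in an affected contrast was about 0.06 to 0.07 SD.

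**The case against.** **The effect may be large enough to absorb the loss.** With f = 0.3 under the G*Power interaction convention and ρ from .50 to .80, power is at least 95.5% at N = 31, 91% at N = 26 and 85% at N = 22. This stands as a qualification. However, for an equal difference at both follow-ups, f = δ/√18, so f = 0.3 means 0.3 × 4.243 = 1.27 SD. Section 9.2 cites d = .90 for earlier fMRI changes, on a scale that may not be the same.

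**Independent loss favours the criticism.** Discomfort in a scanner plausibly recurs in the same person. This stands, and the independent-loss figures are the upper end of the range under per-endpoint deletion.

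**Section 9.3 acts first.** Questionnaires and MRI fall at the same visits, so most missed visits already exclude the participant. MRI eligibility screening (5.1, 8.1) also removes some failures. What remains is mainly scans that are aborted, unusable or missed separately at the imaging site. A reader might infer that the sentence in 9.4.3 alone governs missing MRI data; that goes too far.

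**Bias can be overstated.** A reader might infer that deletion is valid only if scans are missing completely at random, or that IBMT's relaxation training biases the result by changing scanner tolerance in one arm. Neither follows. Missingness that depends only on arm, age or sex does not bias the interaction. Tolerance would also have to be tied to the brain outcome differently by arm, and the documents give no evidence of that. If unrecorded discomfort were tied to the outcome in that way, a mixed model would not be protected either.

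**These are secondary endpoints in an exploratory pilot.** True, and that limits the priority.

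**Conclusion.** The point holds as a modest, avoidable loss of precision on the brain endpoints. Under independent loss of 5/10/15% per scan, deletion costs about 4, 8 and 13 points of power relative to using every usable scan. This shrinks to about 2, 4 and 7 points if half the loss is at person level and to zero if all of it is. The loss rates are assumptions, and the known-covariance approximation somewhat flatters the mixed model.

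Section 9.4.3 does not say whether deletion is per endpoint or across all MRI modalities. If it is across modalities, more participants are lost unless failures coincide. Bias is possible where outcome-dependent missingness differs by arm, but the documents do not show that it is likely.

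**What to change.** In Section 9.4.3, replace repeated-measures ANOVA with case-wise deletion by a linear mixed model (SPSS MIXED, REML). Include arm, categorical visit, arm by visit, age and sex; an unstructured within-person covariance; and small-sample degrees of freedom (Satterthwaite or Kenward-Roger). Use every usable scan from each participant in the analysis population. Keep the interaction F test and the FDR correction across the three endpoints. Report usable scans by arm, visit and modality, so that differential loss can be seen.

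The cost is SAP wording and slightly different syntax, with no new data. The model relies on missingness being explained by observed scans and covariates, and it must estimate the covariance in about 36 participants. It recovers only part of the loss and cannot restore scans never taken, including those not scheduled after discontinuation under Section 7.1.
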